8.2.3.7 Quality of life questionnaires

8.2.3.7.1 ST. GEORGE'S Respiratory Questionnaire

To study the patient's quality of life, the abbreviated Saint George's Respiratory Questionnaire (SGRQ-C) was used. This questionnaire is self-administered. The SGRQ consists of 50 items, where 10 of them are multiple choice and 40 are true or false. This instrument is divided into three domains:

- a) **Symptoms**, which consists of eight items and refers to all symptoms presented due to lung disease; these include cough, sputum production, dyspnea or shortness of breath or breathlessness and wheezing, as well as duration, frequency and severity.
- b) **Activity**, containing 16 true or false questions and refers to activities that are limited due to dyspnea
- c) **Impacts**, which has 26 items and refers to other situations or aspects related to social or psychological functioning affected by the respiratory problems that may alter the patient's lifestyle.

The sum of the three components gives us the total Quality of Life score. Each item in the questionnaire corresponds to a weight or score ([Appendix 1](#)) depending on the option chosen by the subject; for the true-false questions, only those with a true response have a score. The score corresponding to each subject is calculated by sub-scales. For the **Symptoms** component, the scores obtained from all the items in part 1 (questions 1 to 8) are added together, divided by 662.5, and multiplied by 100. In **Activity**, the score obtained in section 2 and section 6 are added (questions 11 and 15), divided by 1209.1 and multiplied by 100. **Impacts** is calculated with the sum of the scores of sections 1, 3, 4, 5 and 7 (questions 9, 10, 12, 13, 14, 16 and 17), divided by 2117.8, and multiplied by 100. The total results from the sum of the score of the three categories and the division of this sum by 3989.4, multiplied by 100. The score ranges from 0 to 100%. The lower the percentage, the higher the quality of life and vice versa: the higher the percentage, the lower the quality of life.

The change in the quality of life of the patients according to the Saint George's questionnaire will be studied, presenting the main measures of central tendency and dispersion (mean, standard deviation, median, minimum, maximum, IR and 95%CI), both for the total score obtained and for the three domains of Symptoms, Activity and Impacts. We will explore whether there are statistically significant differences in the quality of life of patients depending on the severity of COPD and the type of patient using the Student's t-test or its non-parametric equivalent Mann-Whitney U test, depending on the distribution of the variables.

We will examine whether there has been a significant change over time in quality of life, both for the total sample of evaluable patients and in each of the subpopulations established based on the severity of COPD and the type of patient, using the paired Student's t-test or its non-parametric equivalent, the Wilcoxon test.

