### **8.3. Variables**

**Variables to be recorded from previous clinical history and follow up visits (according to Table 1):**

- Consent date
- Subject code
- Demographic and epidemiological data;
- Antropometric data (weight, height, body mass index (BMI), Waist Circumference)
- Smoking habit, alcohol consumption
- Spirometric data (FEV1, FVC, FEV1/FVC)
- Pharmacological treatment
- COPD severity (GOLD)
  - o GRADE 1: Mild/unknown [FEV1≤ 80%, FEV1/FVC < 0,7 or no spirometry data]
  - o GRADE 2: Moderate [50% ≤ FEV1< 80%,FEV1/FVC < 0,7]
  - o GRADE 3: Severe [30% ≤ FEV1 < 50%, FEV1/FVC < 0,7]
  - o GRADE 4: Very severe [FEV1< 30% o FEV1< 50% plus respiratory failure,FEV1/FVC < 0,7]
- Number and severity of exacerbations

Redacted

- Frequency of total exacerbations (moderate and severe) in the previous year and during follow-up (recorded at hospital or primary care level).
- Comorbidities
  - o high blood pressure
  - o dyslipidemia
  - o type 2 diabetes mellitus
  - o metabolic syndrome
  - o heart failure
  - o ischemic heart disease
  - o chronic kidney disease
  - o cirrhosis
- History of neoplasia (solid organ and hematologic)
- Pneumococcal vaccination
- Influenza vaccination
- QoL questionnaire (reduced SGRQ, CAT) - completed by subjects and transcribed into electronic case report form (CRF)

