Secondary endpoints:

- Demographic and epidemiological data;
- Anthropometric data (weight, height, body mass index [BMI], waist circumference)
- Smoking habit, alcohol consumption
- Spirometry data (FEV1, FVC, FEV1/FVC)
- Pharmacological treatment
- Associated comorbidity
 - high blood pressure
 - dyslipidemia
 - type 2 diabetes mellitus
 - metabolic syndrome
 - heart failure
 - ischemic heart disease
 - chronic kidney disease
 - cirrhosis

- History of neoplasia (solid organ and hematologic)
- Pneumococcal vaccination
- Influenza vaccination
- Quality of Life questionnaire (shortened SGRQ, CAT) (completed by the subject and transcribed into the study CRF)

7 **HANDLING OF MISSING VALUES**

In the Saint George Quality of Life scale, ideally there would be no missing values and the questionnaire would be complete; however, if there are missing values, the effect of the missing elements has been examined and the following methods of action are recommended:

Symptoms

The Symptoms component will tolerate a maximum of 2 missed items. The weight for the missed item is subtracted from the total weight for the Symptoms category (662.5) and from the Total weight (3989.4).

Activity

The Activity component will tolerate a maximum of 4 missed items. The weight for the missed item is subtracted from the total weight for the Activity category (1209.1) and from the Total weight (3989.4).

Impacts

The Impacts component will tolerate a maximum of 6 missed items. The weight for the missed item is subtracted from the total weight for the Impacts category (2117.8) and from the Total weight (3989.4).

No criteria for replacement of missing values will be used for the rest of the study variables.

8 **STATISTICAL METHODOLOGY AND STATISTICAL ANALYSIS**

8.1 **STATISTICAL METHODOLOGY**

The results will be evaluated through a cohort study, considering the subjects not vaccinated with PCV13 included in the study as the unexposed group.

- A descriptive analysis of all variables will be performed. Qualitative variables will be analyzed by absolute and relative frequencies. Quantitative variables will be studied using the usual measures of central tendency and dispersion (mean, median, standard deviation, confidence intervals, minimum, maximum and interquartile range).

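### The plan names an abbreviated SGRQ but scores it with the constants of a 50-item form; if the form in use is shorter, the scores are compressed

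*SAP*

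**What the plan says.** **Name of the instrument.** Three places name a cut-down form, and none says that the full form is given.

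- Protocol 8.3 (Variables) lists it as "QoL questionnaire (reduced SGRQ, CAT".
- SAP 6.1 (secondary endpoints) lists it as "Quality of Life questionnaire (shortened SGRQ, CAT".
- SAP 8.2.3.7.1 states that "the abbreviated Saint George's Respiratory Questionnaire (SGRQ-C) was used".

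**Scoring.** Two sentences further on, SAP 8.2.3.7.1 drops the suffix: "The SGRQ consists of 50 items, where 10 of them are multiple choice and 40 are true or false". The domains are Symptoms, "which consists of eight items and refers to all symptoms presented due to lung disease"; Activity, "containing 16 true or false questions and refers to activities that are limited due to dyspnea"; and Impacts, "which has 26 items and refers to other situations or aspects". Summed item weights are divided by 662.5, 1209.1 and 2117.8 for the domains and by 3989.4 for the total, then multiplied by 100. The stated range is 0 to 100%.

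**Missing items.** SAP 7 begins with "The Symptoms component will tolerate a maximum of 2 missed items" and allows 4 for Activity and 6 for Impacts. A missed item's weight is subtracted from the same domain and total denominators.

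**Not visible.** SAP 8.2.3.7.1 refers the item weights to Appendix 1. The SAP appendices are redacted, and the CRF (protocol Annex 2) is listed without content.

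**The concern.** The instrument named and the scoring rule printed do not visibly belong together. An abbreviated form would ordinarily have fewer items than the form it abbreviates, yet every constant in the SAP fits a 50-item questionnaire. If fewer items are asked while the 50-item denominators are kept, even a patient with the worst answer to every question scores below 100.

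Quality of life is secondary objective 2. SAP 8.2.3.7.1 plans means, standard deviations, medians, ranges and 95% confidence intervals for the total and the three domains. All of these depend on the scale. The primary exacerbation analysis, the sample size and the CAT are not touched.

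**Working it through.** **1. Do the SAP's constants agree with one another?** Inputs are from SAP 7 and 8.2.3.7.1.

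- Denominators: 662.5 + 1209.1 + 2117.8 = 3989.4, the stated total.
- Items by domain: 8 + 16 + 26 = 50. Items by type: 10 + 40 = 50.
- Missing-item limits as a share of items: 2/8 = 25%, 4/16 = 25%, 6/26 = 23%; overall 12/50 = 24%.

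The rule is complete and coherent for a 50-item form. No part of it is labelled as belonging to a shorter one.

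**2. What happens if the form is shorter?** Let *w* be the share of the 3989.4 total weight carried by items not on the form, with retained items keeping their weights and absent items not counted as missed. The highest possible total is then 100 × (1 − *w*), and any true difference is multiplied by (1 − *w*). The documents do not give *w*, so the values below are assumptions. The 4-point difference is only an illustration. The item equivalent is 50 × (1 − *w*), at equal average weight.

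| Absent weight *w* | Retained weight | Item equivalent | Maximum total | A true 4.0 shows as |
|---|---|---|---|---|
| 0% | 3989.4 | 50 | 100 | 4.0 |
| 5% | 3789.9 | 47.5 | 95 | 3.8 |
| 10% | 3590.5 | 45 | 90 | 3.6 |
| 20% | 3191.5 | 40 | 80 | 3.2 |

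**3. Domains.** The table is for the total. Each domain has its own factor, which depends on where the absent items fall. Take *w* = 5%, an absent weight of 0.05 × 3989.4 = 199.5. If it is spread in proportion, every domain has a maximum of 95. In the extreme case where it all lies in Symptoms, that domain's maximum is 100 × (662.5 − 199.5)/662.5 = 69.9 and the other two stay at 100.

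**4. Effect on tests.** With complete questionnaires and correct item weights, every patient's domain score is multiplied by the same constant. The planned t, Mann-Whitney and Wilcoxon p-values are then unchanged. Means, differences and confidence limits are not.

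**5. Effect with missed items.** Let *T′* be the shorter form's total weight, *m* the weight a patient missed, and *S* the sum of that patient's answered weights. The proper score is 100 × *S*/(*T′* − *m*); the SAP's rule gives 100 × *S*/(3989.4 − *m*). The ratio is (*T′* − *m*)/(3989.4 − *m*), which varies by patient.

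Take *w* = 10% (*T′* = 3590.5) and missed items of average weight 3989.4/50 = 79.8:

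- No missed items: 3590.5/3989.4 = 0.900.
- 12 missed items, the sum of the three limits (*m* = 957.5): 2633.0/3031.9 = 0.868.

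The factor is then no longer constant, although on this assumption the spread is modest.

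**The case against.** The strongest reply is that the documents never give the abbreviated form's item count and never call the 50-item form the full one. SAP 8.2.3.7.1 can be read as describing one instrument throughout, with SGRQ as shorthand. On that reading the arithmetic closes exactly and only the label is loose. The redacted Appendix 1 and the CRF would be expected to show which form and weights are used. This stands as far as certainty goes: the text does not prove that scores will be mis-scaled. It does not remove the mismatch, because the name, item counts, denominators and limits are all in unredacted text.

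A reader might also infer that patients would be wrongly set to missing because absent items use up the missing-item allowance. The documents do not support this. Nothing in SAP 7 says that items not on the form count as missed. If they did, their weights would be subtracted from the denominators, so within the limits there would be no compression, and beyond them no compressed score would arise. If they do not count, the allowance is untouched. The two harms cannot occur under one reading.

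Finally, the practical effect is limited. Exposed/unexposed and before/after p-values survive a constant rescaling, the documents set no SGRQ responder threshold, and the CAT is a second quality-of-life measure. That is correct, and it keeps this a secondary-endpoint matter. But the sizes of scores and differences are themselves planned results, and they would be wrong.

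**Conclusion.** The point holds in conditional form. The protocol and SAP name an abbreviated SGRQ, while the visible scoring is entirely that of a 50-item form. If the form administered has fewer than 50 items, as its name implies, and absent items are not handled as missed, domain and total scores cannot reach the stated 100%. Means, differences and confidence intervals are then compressed.

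The documents do not fix the amount. Assumed absent weight of 5% to 20% gives a maximum total of 95 to 80, with domain factors possibly different. This rests on retained items keeping their weights. With complete questionnaires, p-values would not change at domain level; score sizes and comparability with other SGRQ results would. With missed items the factor would vary by patient.

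A reader might conclude outright that the SGRQ results will be mis-scaled. The documents stop short of that: if the 50-item form is in the CRF, the scoring is right and only the name is wrong. Either way, one of the two has to be corrected.

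**What to change.** State in the SAP which form is in the CRF, then align the other text with it.

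- **If it is the abbreviated form:** replace the item counts, item weights, denominators and missing-item limits in SAP 7 and 8.2.3.7.1 (and Appendix 1, if it holds other weights) with that form's own scoring. Say that items not on the form are not missed items.
- **If it is the 50-item form:** keep the scoring, and correct the instrument name in protocol 8.3, SAP 6.1 and SAP 8.2.3.7.1.

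The cost is wording and, in the first case, a change to the scoring program. No new data are needed, and the primary analysis is unaffected.

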## 7. RESEARCH QUESTION AND OBJECTIVES

- **Primary objectives**

1. Evaluate the impact of routine clinical practice vaccination with PCV13 on the reduction of the risk of COPD moderate/severe exacerbations (see definitions) in adults, after 2 years of follow up.
2. Determine which subgroup of patients (based on the severity of COPD) benefit most from vaccination with PCV13  
COPD severity (GOLD)
  - GRADE 1: Mild/unknown [FEV1≤ 80%, FEV1/FVC < 0,7 or no spirometry data]
  - GRADE 2: Moderate [50% ≤ FEV1< 80%, FEV1/FVC < 0,7]
  - GRADE 3: Severe [30% ≤ FEV1 < 50%, FEV1/FVC < 0,7]
  - GRADE 4: Very severe [FEV1< 30% o FEV1< 50% plus respiratory failure, FEV1/FVC < 0,7])

- **Secondary objectives**

1. Evaluate the impact of influenza and PCV13 vaccination on the reduction of the risk of exacerbations
2. Evaluate the impact of vaccination with PCV13 on patients' quality of life
3. Evaluate the impact of vaccination with PCV13 on the decrease of FEV1
4. Estimate the potential economic savings for the healthcare system derived from vaccination of COPD patients with PCV13
5. Determine the prevalence of PCV13 vaccination in COPD patients.

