8.2.3.2 Change in post-bronchodilator spirometry test

Changes in the spirometry data at the different follow-up visits will be given and analyzed using the main measures of central tendency and dispersion (mean, median, standard deviation, confidence intervals, minimum, maximum and interquartile range).

- FEV1
- FVC
- FEV1/FVC

The study will examine whether there has been a significant change in the spirometry data over time, both in the total sample of evaluable patients and in each of the subpopulations established based on the severity of the COPD and type of patient, using the Student's t-test for paired data or its non-parametric equivalent, the Wilcoxon test. The % reduction in the parameters FEV1, FVC and FEV1/FVC will be calculated at the 24-month visit relative to baseline ((final value-baseline value)*100/baseline value).

The Student's t-test, one-way ANOVA or its non-parametric equivalents, the Mann-Mann U test or Kruskal-Wallis H test will be used in order to determine if statistically

significant differences in FEV1, FVC, FEV1/FVC (% reduction compared to the FEV1, FVC and FEV1/FVC baseline values) are observed, depending on the severity of the COPD and type of patient (exposed/unexposed).

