8.2.3.7.2 CAT

Questionnaire used to measure the impact COPD (chronic obstructive pulmonary disease) is having on the patient's wellbeing and daily life. The answers and test score can be used by the patient and the healthcare professional to help improve the management of the COPD and get the greatest benefit from treatment.

The study will look at the change in the quality of life of the patients according to the CAT questionnaire, presenting the main measures of central tendency and dispersion (mean, standard deviation, median, minimum, maximum, IR and 95%CI), for the total score obtained as the sum of the scores obtained in the 8 items that compose it.

We will study whether there are statistically significant differences in the quality of life of patients depending on the severity of COPD and the type of patient using the Student's t-test or its non-parametric equivalent Mann-Whitney U test, depending on the distribution of the variables.

We will study whether there has been a significant change over time in quality of life, both for the total sample of evaluable patients and in each of the subpopulations established based on the severity of COPD and the type of patient, using the paired Student's t-test or its non-parametric equivalent, the Wilcoxon test.

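### SAP 8.2.3.7 specifies no between-cohort test of change in SGRQ or CAT; read literally, it compares scores unadjusted for baseline, so a baseline difference could pass as a PCV13 effect

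*SAP*

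**What the plan says.** The objective is stated in Protocol section 7 and repeated in SAP 2.2: "Evaluate the impact of vaccination with PCV13 on patients' quality of life". The endpoint list in SAP 6.1 only names the instruments: "Quality of Life questionnaire (shortened SGRQ, CAT").

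The analysis is in SAP 8.2.3.7.1 and 8.2.3.7.2, which share one structure:

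- Change is announced and summarised descriptively. For SGRQ: "The change in the quality of life of the patients according to the Saint George's questionnaire will be studied". For CAT: "The study will look at the change in the quality of life of the patients according to the CAT questionnaire".
- The cohorts are compared on quality of life without further definition, by t-test or Mann-Whitney. The SGRQ section states: "We will explore whether there are statistically significant differences in the quality of life of patients depending on the severity of COPD and the type" (exposed or unexposed). The CAT section uses the same tests: "We will study whether there are statistically significant differences in the quality of life of patients depending on the severity of COPD and the type" (again exposed or unexposed).
- Change over time is tested with a paired t-test or Wilcoxon test, in the total sample and within each severity or exposure subpopulation.

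SAP 8.2.3.2 treats spirometry differently. It defines the percentage change from baseline to month 24 and tests by type of patient whether differences in the % "reduction compared to the FEV1, FVC and FEV1/FVC baseline values) are observed".

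Protocol Table 1 schedules the questionnaires at months 0, 12 and 24. Protocol 8.2 says that vaccination follows clinical practice and may take place before or after inclusion.

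**The concern.** An impact of PCV13 on quality of life, estimated from two cohorts, needs a between-cohort contrast that allows for where each cohort started. Vaccination is not randomised. Under Protocol 8.1 the controls include patients who were not recommended the vaccine, patients who did not receive it despite a recommendation, and patients with contraindications. Their SGRQ and CAT scores may differ from those of vaccinated patients before any vaccine effect.

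An unadjusted comparison of scores carries such a difference into the answer. The within-cohort paired tests cannot replace the missing contrast, because a significant change in one cohort and a non-significant change in the other is not evidence that the changes differ. At stake is the answer to secondary objective 2; the primary objectives are not affected.

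**Working it through.** **Does another section supply the contrast?**

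| Place | What is compared between exposed and unexposed | Baseline used? |
|---|---|---|
| SAP 8.2.3.2, spirometry | % change from baseline to month 24 | Yes |
| SAP 8.2.3.7.1, SGRQ | Quality of life; no visit or change named | No |
| SAP 8.2.3.7.2, CAT | Quality of life; no visit or change named | No |
| SAP 8.2.2, baseline tables | Demographics, anthropometry, alcohol, history; not SGRQ or CAT | n/a |
| SAP 8.1 and 8.2.3.1, multivariable models | Logistic models for exacerbations or exacerbator status only | n/a |

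No section provides a baseline-adjusted quality-of-life contrast or a between-cohort test of change.

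**Inputs for an illustration.** The plan gives no quality-of-life sample size, effect or power, so there is no figure to reproduce.

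- From SAP section 5: 540 × 0.7 = 378 and 378 × 0.7 ≈ 264 exposed; 1000 × 0.7 = 700 and 700 × 0.7 = 490 unexposed.
- From SAP section 4: significance at p < 0.05. Sidedness is not stated; two-sided is used.
- Assumed: SGRQ SD 15, 20 or 25; baseline gap 4 points; correlation r = 0.7 between baseline and follow-up; true vaccine effect zero.

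The point values apply to SGRQ only. SGRQ runs from 0 to 100 and CAT is a sum of eight items, so one SD cannot serve both.

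**Test on score levels, gap persists.** SE = SD × √(1/264 + 1/490) = SD × 0.0763. The probability of significance is approximately Φ(gap/SE − 1.96).

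| SD | SE | gap/SE | Significant |
|---|---|---|---|
| 15 | 1.15 | 3.49 | 94% |
| 20 | 1.53 | 2.62 | 75% |
| 25 | 1.91 | 2.10 | 55% |

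At SD 20, gaps of 2 and 6 points give 26% and 98%. If the 4-point gap shrinks to 0.7 × 4 = 2.8 points by follow-up, 2.8/1.53 = 1.83 and the level test is significant in 45% of studies.

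**Two possible replacements, SD 20, 4-point gap, r = 0.7.**

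- Adjustment for baseline: SE = 1.53 × √(1 − 0.49) = 1.09. If the gap persists, the remaining bias is 4 × (1 − 0.7) = 1.2, the ratio is 1.10 and 20% are significant. If the gap shrinks to 0.7 of its size, the bias is 0 and the rate is 5%.
- Change from baseline: SD of change = 20 × √(2 × 0.3) = 15.5 and SE = 1.18. If the gap persists, the bias is 0 and the rate is 5%. If it shrinks to 0.7, the bias is 1.2, the ratio is 1.01 and 17% are significant.

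A simulation of 4,000 studies with the persisting gap gave 74.8% for levels, 19.5% for baseline adjustment and 4.8% for change. At r = 0.5 the baseline-adjusted figure rose to 33%.

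**Within-cohort paired tests.** Suppose both cohorts truly change by the same 2 points (SD 20, r = 0.7). Exposed: SE = 15.5/√264 = 0.95, significant in 55%. Unexposed: SE = 15.5/√490 = 0.70, significant in 82%. With independent cohorts the two verdicts disagree in 0.555 × 0.185 + 0.815 × 0.445 = 47% of studies, although the changes are identical.

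**The case against.** The SAP never says that levels are compared. In the SGRQ section the between-cohort sentence follows directly on the one announcing change, and a reader could carry change over from it. That reading is possible. The contrast with 8.2.3.2, where the change variable and month 24 are written out, makes the literal reading the better supported one. On the lenient reading the variable, visit and covariates are still undefined, so the text needs repair either way.

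SAP 8.2.1 asks for the analysis split by exposure, and section 9 lists quality-of-life output under that split. A by-visit table could therefore show a baseline gap. That stands as partial mitigation: the gap would be seen, but not allowed for in the test.

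The illustration rests on an SD, gap and correlation that the documents do not give. This also stands; the figures show sensitivity and do not predict what the study will find.

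Finally, no single replacement is clean. Baseline adjustment and change scores each fail in the case where the other works, and neither removes confounding by factors outside the model. For patients vaccinated before inclusion, the Visit 0 score and GOLD grade are already post-exposure, so adjusting for them could remove part of the effect. These points stand and shape the fix.

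**Conclusion.** The between-cohort quality-of-life contrast is under-specified. On its literal reading it lets a baseline difference between non-randomised cohorts pass as a PCV13 effect. For SGRQ, with 264 v 490 patients, no vaccine effect and a persisting 4-point gap, the level test is significant in 94%, 75% or 55% of studies at SD 15, 20 or 25, against a nominal 5%. Gap and SD are assumptions.

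A reader might infer three stronger things that the documents do not support:

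- That the SAP certainly tests score levels at month 24. It names neither a level nor a visit.
- That the SAP formally defines the endpoint as change. Section 6.1 names only the questionnaires; change appears in the analysis text.
- That the sponsor will answer the objective by setting the two paired tests side by side. Nothing says so; the 47% disagreement only shows why that would not be a substitute.

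Nor do the documents show that a baseline gap exists; non-random vaccination makes one plausible. The objective is secondary and the repair is cheap, so the change should be made.

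**What to change.** In SAP 8.2.3.7.1 and 8.2.3.7.2:

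1. Replace the exposed/unexposed test on the score with a linear model for the month-24 score, and likewise month 12, for SGRQ total, SGRQ domains and CAT. Include PCV13 exposure, the Visit 0 score of the same questionnaire, GOLD grade, and the factors that SAP 8.1 already lists for exacerbations, such as smoking, comorbidities and influenza vaccination. Report the adjusted mean difference with 95% CI as the answer to secondary objective 2.
2. Add the between-cohort comparison of change from Visit 0 as a sensitivity analysis. If the two disagree, say that the conclusion depends on how the baseline gap would have evolved without vaccination.
3. Define baseline relative to vaccination. Run the main contrast in patients not yet vaccinated with PCV13 at Visit 0, or report those vaccinated before inclusion separately.
4. Keep the within-cohort paired tests as descriptive.

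The cost is SAP wording and one regression per score and visit, on data already scheduled at months 0, 12 and 24. Patients without a baseline questionnaire drop out of the main contrast, and those vaccinated before inclusion leave it or are shown separately, so precision falls. Residual confounding remains and should be stated with the result.
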